# Sample Size Calculation (1) :

The sample size calculation was planned for the ratio of 2:1. The SAS 9.4 statistical software, was used to calculate the sample size needed for the study under the assumption of a non-inferiority trial for binary outcome endpoint.

According to the recommendations for the co-primary endpoints, the sample size OVED

- The difference in seroconversion rate of active comparator vaccine and MITTEE Seroconversion rate of GPO Tri Fluvac should not exceed 10 percentage points.

- The difference in natural log of mean antibody titer between active comparator vaccine and GPO Tri Fluvac should not exceed 0.405, which is equivalence to the margin for GMT ratio = 1.5.

The sample size calculation was calculated using parameters of three strains of influenza under the study, including H1, H3, and Flu B. The parameter estimates for seroconversion and Standard deviation of natural log of antibody titer were obtained from previous study, phase II study of GPO Tri Fluvac.

Influenza strain	Titer Visit	Treatment Group	Sero- conversion	Mean of ln(titer)	
H1	Day 21	Vaccine	0.88	5.9728	
Н3	Day 21	Vaccine	0.535	5.36976	
Flu B	Day 21	Vaccine	0.865	4.75286	

The sample size calculation for non-inferiority test for proportions was performed with the margin of 0.1, assuming different seroconversion rate of the three influenza strain, and expected difference in seroconversion of the two groups is 0.000 with one-sided test alpha level 0.025 and power 0.8. Finally the sample size was adjusted for 7% not included in the ATP cohort. The required sample size for the study is as follow. The largest sample size required is 945 for total: 630 for study vaccine group and 315 for comparator vaccine group.

I wo group test of equivalence in proportions (large unequal n's)						
	H1	H3	Flu B			
Test significance level, α	0.025	0.025	0.025			
(one- sided)						
Standard proportion, $\pi_{S}$	0.880	0.535	0.865			
Equivalence limit difference,	0.100	0.100	0.100			
$\pi_{\rm T}$ - $\pi_{\rm S}$ , $\Delta_0$						
Test expected proportion, $\pi_T$	0.880	0.535	0.865			
Expected difference, $\pi_T - \pi_S$ , $\Delta_1$	0.000	0.000	0.000			
Power ( % )	80	80	81			
n S	125	293	134			
n T	250	586	276			
Ratio: n T / n S	2.000	2.000	2.000			
$N = n_S + n_T$	375	879	414			
Adjusted 7% not included in the AT	P cohort					
n S	134	315	148			
n T	268	630	296			

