## Assessment of immune response

According to WHO and FDA guidelines, the antibody titres to corresponding vaccine strain of influenza virus will be analyzed by comparison of paired serums using HI assay.

The serum samples will be collected on Days 0 prior to vaccination, Day 21, and Day 90 and will be analyzed for presence of influenza-specific antibody using Hemagglutination Inhibition (HI) assay. HI antibody titers will be compared between pre- and post-vaccination serum samples.

Percentages of subjects with each immune response will be calculated along with 95% CIs using exact statistical methods. Geometric mean titers (GMTs) along with 95% CIs will also be calculated using the t-test. No multiplicity adjustment to the error rate, alpha, will be made.

The primary immunogenicity endpoint is based on the ATP cohort, and NI conclusion will be based on the outcome of this analyses.

The primary immunogenicity endpoints and analysis are as follows:

- Number and percentage of participants with seroconversion against each of the three vaccine antigens. Seroconversion is defined as a serum HI antibody titer meeting the following criteria:
  - Pre-vaccination titer <1:10 and a post-vaccination titer measured on Day 21 of ≥1:40; or

  - Pre-vaccination titer ≥1:10 and at least a four-fold increase in post-vaccination measured on Day 21.
- Geometric mean titers (GMTs) of serum HI antibodies pre- (Day 0) and post-vaccination (Day 21) for each of the three vaccine antigens.

In assessing the non-inferiority, the upper bound of the two-sided 95% CI on the difference between the seroconversion rates (Seroconversion rate of active comparator vaccine – Seroconversion rate of GPO Tri Fluvac) should not exceed 10 percentage points. For the other primary endpoint, the upper bound of the two-sided 95% CI on the ratio of the GMTs (GMT active comparator vaccine/GMT GPO Tri Fluvac) should not exceed 1.5.

In addition, the secondary immunogenicity endpoints and analysis include the following:

- Number and percentage of participants with a HI antibody titer ≥1:40 (seroprotective level) to each of the three vaccine antigens measured on Day 21 and Day 90.
- Number and percentage of participants who develop at least a four-fold increase in HI antibody titers to each of the vaccine antigen post-vaccination measured on Day 21 and Day 90 segregated by pre-vaccination HI antibody titers (<1:10 or ≥1:10).

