The proportions of seroconversion responders, at Day 21 between groups (vaccines or comparator) will be examined and compared to determine the effect of an inactivated trivalent influenza vaccine. The antibody titers of each group will also be presented as GMT. The 95% CI and *p*-value will be calculated and presented. Multivariate analysis will be performed as needed to explore potential confounders.

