Appendix 06: Listing of Adverse Event	. 78
Appendix 07: Listing of Illness like Influenza (ILI)	. 78
Appendix 08: Listing of Concomitant Medication	. 79
Appendix 09: List of HAI Assay (Flu A H1 Antigen)	. 80
Appendix 10: List of HAI Assay (Flu A H3 Antigen)	. 80

Study Synopsis

Title: A Phase II/III Double Blinded, Randomized, Controlled, Non-inferiority trial to evaluate the Immunogenicity and Safety of Tri Fluvac, a Seasonal Trivalent Inactivated split virion Influenza vaccine, in healthy Thai subjects aged 18 – 49 years.

Protocol #: GPO Tri Fluvac Vaccine Phase II/III

Description of Study Design:

This is a phase II/III, non-inferiority double-blinded, randomized, controlled trial of immunogenicity, safety and preliminary efficacy with two groups of participants who will received a seasonal trivalent split, inactivated influenza vaccine (A/H1N1; A/H3N2 and B) or an active comparator (licensed influenza vaccine).

A total of about 945 healthy Thai male and female adult volunteers 18 through 49 years of age; 630 participants will be randomized to receive vaccine and 315 will receive an active comparator (a 2:1 ratio) (inclusion of \sim 7% lost to follow-up).

Safety will be assessed for all participants through Day 90 after vaccination. Immunogenicity will be assessed in serum samples obtained at baseline and 21 days after vaccination in a subset of at least 630 individuals randomized to study vaccine and 315 active comparator vaccine recipients.

Study Hypothesis:

Immunogenicity: A single dose of the GPO seasonal trivalent split, inactivated influenza vaccine will induce immune responses measured by HI assay to each of the three vaccine antigens and will be non-inferior to active licensed comparator vaccine.

Safety: A single dose of the GPO seasonal trivalent split, inactivated influenza vaccine will be safe and well tolerated in adults 18 to 49 years of age.

Study Objectives:

Primary objective

Immunogenicity:

To evaluate the immunological non-inferiority seroconversion rate (using HI assay) and Geometric Mean Titre (GMT) of the GPO seasonal trivalent split, inactivated influenza vaccine compared to active comparator vaccine for each of the three vaccine antigens, three weeks after immunization (Day 21) and at the end of follow up period (Day 90).

Safety:

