Counts and percentages of subjects with solicited local and systemic reactions during the three days post-injection. In addition, all adverse events (AE) and serious adverse events (SAEs), and new onset of chronic diseases (NOCDs) will be collected for the entire study period. Specifically, the following safety parameters will be monitored and analyzed in terms of the number and proportion of participants reporting the following events will be assessed:

- Solicited local adverse events, including redness/erythema, swelling/induration, pain and limitation of arm movement within 30 minutes of vaccination and over the 3-day period post vaccination (Day 0-3).

- Solicited systemic adverse events, including fever, fatigue/malaise, muscle aches, joint aches, chills, nausea and headache within 30 minutes of vaccination and over the 3-day period post vaccination (Day 0-3).

- Unsolicited adverse events (AEs) occurring within 90 days post vaccination.

- Serious Adverse Events (SAE) occurring during the entire study period (Days 0-90).

Counts of all events will be reported and summarized according to event severity, as "any local AE", or "any systemic AE", and by relationship to administration of study product, as deemed by a blinded study clinician. Percentages of participants experiencing each reaction or event, or at least one reaction or event will be calculated along with two-sided exact 95% CIs. The percentage of participants with solicited AE and SAEs will be compared between vaccine and comparator groups and a two-sided p-value of 0.05 will be considered statistically significant.

Inferential analyses

GMT ratios (GMT active comparator vaccine/GMT GPO TRI FLUVAC) and difference of seroconversion rate (with two-sided 95% CI) related to the comparisons of interest will be computed. Acceptance value of GMT ratios at \leq 1.5 and/or difference of seroconversion rate at \leq 10% for the upper bound of the 95% CI will be considered for non-inferiority.

Secondary Immunogenicity Endpoints and analysis:

The secondary immunogenicity endpoints will be analyzed by the following:

- Number and percentage of participants with a HI antibody titer $\geq 1:40$ (seroprotective level) to each of the three vaccine antigens measured on Day 21 and Day 90.

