	Tri fluvac (N = xx)	Comparator (N = xx)	Tri fluvac (N = xx)	Comparator (N = xx)	Tri fluvac (N = xx)	Comparator (N = xx)	Tri fluvac (N = xx)	Comparator (N = xx)
Min, Max								
P- value =								

	D	Day 0 Day 7		Day 21		Day 90		
	Tri fluvac (N = xx)	Comparator (N = xx)	Tri fluvac (N = xx)	Comparator (N = xx)	Tri fluvac (N = xx)	Comparator (N = xx)	Tri fluvac (N = xx)	Comparator (N = xx)
HEENT, n (%)								
Normal	xx(xx.xx)	xx(xx.xx)						
Abnormal	xx(xx.xx)	xx(xx.xx)						
P- value =	X.2	xxxx						
Lungs, n (%)								
Normal								
Abnormal								
P- value =								
Cardiovascular, n (%)								
Normal								
Abnormal								
P- value =								
Gastrointestinal, n (%)								
Normal								
Abnormal								
P- value =								
Musculoskeletal, n (%)								
Normal								
Abnormal								
P- value =								
Skin, n (%)								
Normal								
Abnormal								
P- value =								

TREF 3.4: Physical Examination by GPO Tri Fluvac and Active Comparator Group

	Day 0		D	Day 7		Day 21		Day 90	
	Tri Fluvac (N = xx)	Comparator (N = xx)	Tri Fluvac (N = xx)	Comparator (N = xx)	Tri Fluvac (N = xx)	Comparator (N = xx)	Tri Fluvac (N = xx)	Comparator (N = xx)	
Neurologic, n (%)	X	((
Normal	xx(xx.xx)	xx(xx.xx)							
Abnormal	xx(xx.xx)	xx(xx.xx)							
P- value =	X XXXX								

TREF 3.4: Physical Examination by GPO Tri Fluvac and Active Comparator Group (Continue)

TREF 3.5: Comparison of Maximum Grade of Any Local Reaction at Post Immunization by GPC
Tri fluvac and Active Comparator Group

Grade		Tri Fluvac (N = xx) n (%)	Comparator (N = xx) n (96)
Grada 0			
Grade 0		XX(XX.XX)	XX(XX.XX)
Grade 1		XX(XX.XX)	XX(XX.XX)
Grade 2		xx(xx.xx)	xx(xx.xx)
Grade 3		xx(xx.xx)	xx(xx.xx)
P- value =	X.XXXX		

Note: - Any local reaction on any day (by case)

- Erythema and Induration will be not included.

- Grading

- Grade 0 none
- Grade 1 mild
- Grade 2 moderate
- Grade 3 severe

TREF 3.6: Comparison of Local Reaction at Post Immunization each Follow up Time by GPO Tri Fluvac and Active Comparator Group

	30	min	D	Day 1	D	ay 2	Da	ny 3
Local Reaction	Tri Fluvac	Comparator						
	(N=xx)							
- Pain, n (%)	xx(xx.x)	xx(xx.xx)						
p-value =	X.:	xxxx						
- Limitation of arm movement, n (%)								
p-value =								
- Erythema (cm.)								
n								
Mean(SD)								
Median								
Min, Max								
p-value =								
- Swelling (cm.)								
n								
Mean(SD)								
Median								
Min, Max								
p-value =								
- Induration (cm.)								
n								
Mean(SD)								

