Grade 0 - none Grade 1 - mild Grade 2 - moderate Grade 3 - severe TREF 3.11: Comparison of Systemic Reaction at Post Immunization each Follow up Time by GPO Tri fluvac and Active Comparator Group

	30 min.		Day 1		Day 2		Day 3	
Systemic Reaction	Tri	Comparator	Tri fluvac	Comparator	Tri fluvac	Comparator	Tri fluvac	Comparator
	fluvac	(N=xx)						
- Headache, n (%)	xx(xx.xx)	xx(xx.xx)						
p-value =	Х	X.XXXX						
- Fatigue, n (%)								
p-value =								
- Malaise, n (%)								
p-value =								
- Chills, n (%)								
p-value =								
- Myalgia, n (%)								
p-value =								
- Arthralgia, n (%)								
p-value =								
- Nausea, n (%)								
p-value =								
- Vomiting, n (%)								
p-value =								
- Rash, n (%)								
p-value =								

Note: Summary by case who had symptoms

Systemic I	Reaction	Tri fluvac	Comparator
		(N=XX)	(N=XX)
Headache,	n (%)		
Grade 0		XX(XX.XX)	xx(xx.xx)
Grade 1		xx(xx.xx)	xx(xx.xx)
Grade 2		XX(XX.XX)	XX(XX.XX)
Grade 3		XX(XX.XX)	XX(XX.XX)
	p-value = x	XXXX	
Fatigue, n (%)		
Grade 0			
Grade 1			
Grade 2			
Grade 3			
	p-value =		
Malaise, n ((%)		
Grade 0			
Grade 1			
Grade 2			
Grade 3			
	p-value =		
Chills, n (%	ы 1		
Grade 0	•)		
Grade 1			
Grade 2			
Grade 3			
	p-value =		
Myaloia n	(%)		
Grada 0	(70)		
Grade 1			
Grade 1			
Grade 2			
Glade 5	n-value =		
Authualais	p-value -		
Arturaigia,	ш (%)		
Grade 0			
Grade 1			
Grade 2			
Grade 3			
	p-value =		

TREF 3.12: Comparison of Maximum Grade of Systemic Reaction by Symptom at Post Immunization by GPO Tri fluvac and Active Comparator Group

Systemic Reaction	Tri fluvac (N=xx)	Comparator (N=xx)
Nausea, n (%)		
Grade 0	XX(XX.XX)	xx(xx.xx)
Grade 1	xx(xx.xx)	xx(xx.xx)
Grade 2	XX(XX.XX)	xx(xx.xx)
Grade 3	XX(XX.XX)	xx(xx.xx)
p-value =		
Vomiting, n (%)		
Grade 0		
Grade 1		
Grade 2		
Grade 3		
p-value =		
Rash, n (%)		
Grade 0		
Grade 1		
Grade 2		
Grade 3		
p-value =		

TREF 3.12: Comparison of Maximum Grade of Systemic Reaction by Symptom at Post Immunization by GPO Tri fluvac and Active Comparator Group (Continue)

- Note: On any day (by cases)
 - Grading
 - Grade 0 none Grade 1 - mild Grade 2 - moderate Grade 3 - severe

Number of Days by Systemic Reaction		ion Tri fluvac	Comparator
Haadaaba	only 20 min	(IN-XX)	(N-XX)
пеацасце	omy 50 mm.		XX(XX.XX)
		XX(XX.XX) XX(VX XX)	XX(XX.XX) XX(XX.XX)
	2 days	•••(••••••)	лл(лл.лл) vv(vv vv)
	3 days	~~~~~~~~~~~~~~~~~~~~~~~~~~~~~~~~~~~~~~	лл(лл.лл) vv(vv vv)
	4 days		XX(XX.XX)
	5 days	XX(XX.XX)	XX(XX.XX)
	p-value =	X.XXXX	

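### The primary safety comparison rests on a p<0.05 rule alone; no between-arm risk difference or confidence interval for it is planned

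*SAP*

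**What the plan says.** Protocol Section 3 (Primary Safety) and the SAP synopsis make the between-arm comparison of solicited symptoms, AEs and SAEs part of the primary safety objective. Both documents also hypothesise that the vaccine will be safe and well tolerated.

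For that comparison, the SAP synopsis (Primary Safety Endpoints) says that the percentages with solicited AEs and SAEs "will be compared between vaccine and comparator groups and a two-sided p-value of 0.05 will be considered statistically significant". The protocol summary and protocol 11.4 carry the same rule. No test is named. The same paragraph plans intervals on the percentages: those with each reaction, "or at least one reaction or event will be calculated along with two-sided exact 95% CIs".

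The shells apply p-values reaction by reaction. TREF 3.6 is titled "Comparison of Local Reaction at Post Immunization each Follow up Time by GPO Tri" Fluvac and Active Comparator Group, and TREF 3.11 "Comparison of Systemic Reaction at Post Immunization each Follow up Time by GPO" Tri fluvac and Active Comparator Group. TREF 3.5 and 3.10 compare the maximum grade of any local and any systemic reaction. They print counts, percentages and a p-value, and a note to TREF 3.5 leaves out erythema and induration.

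On multiplicity, the protocol says under Assessment of immune response: "No multiplicity adjustment to the error rate, alpha, will be made". Nothing is said for safety.

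On SAEs, protocol 11.4 first rules out statistical testing of unsolicited AEs, SAEs included, and in its next sentence compares SAEs at p 0.05. TREF 2.1, the SAE summary shell, has no p-value.

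**The concern.** A comparative objective needs an estimate of the difference and its uncertainty. Here the reader gets a percentage for each arm and a p-value. Two things follow.

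First, with many unadjusted p-values and no comparison named as the main one, an isolated small p-value in one reaction on one day has no agreed weight. Some are expected by chance even if the two vaccines are equally reactogenic.

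Second, and more important, the objective is served by showing that any excess is small. A p-value above 0.05 does not show this. It is compatible with an excess large enough to matter, and the planned output does not say how large. For immunogenicity the SAP does give the difference and the ratio with 95% CI (TREF 02-04), so the other primary objective is reported to a lower standard.

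**Working it through.** **Inputs**

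- Arm sizes 630 and 315 (SAP synopsis: "630 participants will be randomized to receive vaccine and 315 will receive an active comparator (a 2:1 ratio").
- Two-sided 0.05 for safety (SAP synopsis).
- Reaction rate 32.5%: injection-site pain in the vaccine arm of the earlier phase I/II trial (protocol 2.4). Using it as the comparator rate here is an assumption; lower rates are shown below.
- Number of p-values: counted from the SAP shells.

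**The plan's own sample size.** It is driven by H3 seroconversion: "expected difference in seroconversion of the two groups is 0.000 with one-sided test alpha level 0.025 and power 0.8", rate 0.535, margin 0.10, ratio 2:1.

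n(comparator) = (1.96 + 0.842)² × 0.535 × 0.465 × (1 + 1/2) / 0.10² = 292.9, so 293, with 586 for Tri Fluvac. Dividing by 0.93 gives 315.05 and 630.1, against 315 and 630 stated. The arms were sized for non-inferiority of seroconversion; no safety comparison entered the calculation.

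**Count of reaction-level p-values**

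| Shell | p-values |
|---|---|
| TREF 3.2 (4 times) | 4 |
| TREF 3.5 | 1 |
| TREF 3.6 (5 reactions × 4 times) | 20 |
| TREF 3.7 | 2 |
| TREF 3.8 | 2 |
| TREF 3.9 | 1 |
| TREF 3.10 | 1 |
| TREF 3.11 (9 reactions × 4 times) | 36 |
| TREF 3.12 | 9 |
| TREF 3.13 | 9 |
| TREF 3.14 | 0 |
| Total | 85 |

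If TREF 3.6 and 3.11 carry one p-value per row, they contribute 5 and 9, and the total is 85 − 15 − 27 = 43.

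**Chance signals if the vaccines are equally reactogenic.** 85 × 0.05 = 4.25; 43 × 0.05 = 2.15. Correlation between the tests does not change these expected counts. They are ceilings, because tests on rare events run below their nominal level. If Fisher's exact test is assumed (the documents name none), its true size at 630:315 is about 0.9% at a 0.2% event rate and 3.4% at a 1% rate.

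**What p>0.05 leaves open.** With the same rate p in both arms, the 95% half-width for the difference is 1.96 × √[p(1 − p)(1/630 + 1/315)]. At p = 0.325 this is 1.96 × √(0.2194 × 0.004762) = 0.063, or 6.3 points.

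Power for a 5-point excess (37.5% against 32.5%):

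- pooled rate = (0.375 × 630 + 0.325 × 315)/945 = 0.3583, null SE = 0.0331;
- SE under the alternative = √(0.375 × 0.625/630 + 0.325 × 0.675/315) = 0.0327;
- power = Φ[(0.05 − 1.96 × 0.0331)/0.0327] = Φ(−0.45) ≈ 0.32.

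If exactly those percentages were observed, the interval would be 5 ± 1.96 × 3.27 points, that is −1.4 to 11.4. The planned output would report this only as not significant.

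| Assumed comparator rate | 95% CI half-width (points) | Excess with 80% power (points) |
|---|---|---|
| 1% | 1.35 | 3.2 |
| 5% | 2.95 | 5.25 |
| 10% | 4.06 | 6.65 |
| 32.5% | 6.33 | 9.4 |

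**The case against.** The strongest reply is that this is a reporting refinement, and that most of what is needed is already there. Exact 95% CIs are planned on the percentage with each reaction and with at least one reaction. TREF 3.5 and 3.10 already compare the arms on any local and any systemic reaction. An interval also leaves precision unchanged; the power figures describe the sample size. All of this stands. A reader might infer that the safety results carry no intervals at all, and that would be wrong. What is missing is the between-arm difference and its interval, which cannot be judged reliably by setting two separate intervals side by side.

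The count of 85 also needs care. The 0.05 sentence speaks of percentages with solicited AEs and SAEs. Twelve of the 85 cells compare diameters, and twelve concern vomiting or rash, which the SAP's solicited list does not include. Several shells re-express the same diary data. So 85 is the number of p-values printed, not the number of tests that the rule strictly governs, and 4 chance signals is an upper figure.

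A reader might go further, since the SAP also prints between-arm p-values for immunogenicity (84 cells in TREF 01 and 4.1-4.10), and protocol 11.5 has seroconversion "compared to determine the effect of an inactivated trivalent influenza vaccine". It is tempting to say that these contradict the non-inferiority verdict. The documents do not support that. Eighteen of the 84 repeat other cells, leaving 66. The protocol's Assessment of immune response and TREF 02-04 rest non-inferiority on intervals against the margins. A GMT ratio whose interval lies between 1 and 1.5 is both significantly different and non-inferior; the two statements are compatible.

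**Conclusion.** The concern holds as a limited point. The primary safety comparison has a significance rule but no planned estimate of the between-arm difference, no interval for it, and no comparison named as the main one. Up to 85 reaction-level p-values are printed (43 on the narrower reading of the layout), with at most about 4 chance signals expected under equal reactogenicity. A non-significant result is weak evidence of similar reactogenicity: at a 32.5% rate and full arms, power for a 5-point excess is about 32%, and the interval spans 6.3 points either side.

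These figures assume that all 630 and 315 participants contribute, that large-sample formulas apply, and that the earlier trial's vaccine-arm pain rate is a fair stand-in for the comparator. At lower rates the intervals are narrower, as tabulated. The gap changes neither the data collected nor the immunogenicity conclusion; it is a worthwhile, low-cost improvement to the safety reporting.

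**What to change.** - In protocol 11.4 and the SAP safety text, name any solicited local reaction and any solicited systemic reaction, Day 0-3, as the main safety comparisons.
- In TREF 3.5 and 3.10 add the risk difference (Tri Fluvac minus comparator) with its 95% CI, and state the interval method.
- Reconcile the TREF 3.5 note that drops erythema and induration with the SAP's solicited local list, which contains both, so that any solicited local reaction has one meaning.
- Label the reaction-by-day p-values (TREF 3.2, 3.6, 3.11) as descriptive, with no significance claim attached.
- Show the same risk difference and interval for SAEs in TREF 2.1. Reconcile the two sentences in protocol 11.4 on whether SAEs are tested, and align the SAP synopsis with the result.

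The cost is a few table rows and some sentences in 11.4 and the SAP, and individual p-values will carry less weight in the report. No new data or participants are needed.

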# **3. HYPOTHESIS, OBJECTIVES AND ENDPOINTS**

# **Study Hypothesis:**

A single dose of the GPO seasonal trivalent split, inactivated influenza vaccine will induce immune responses to each of the three vaccine antigens and will be non-inferior to active comparator vaccine.

- The upper bound of the two-sided 95%CI on the ratio of the GMTs (GMT licensed vaccine/ GMT GPO Tri Fluvac) should not exceed 1.5 for each of the three vaccine antigens.
- The upper bound of the two-sided 95% CI on the difference between the seroconversion version VED rates (Seroconversion licensed vaccine Seroconversion GPO Tr Finvac) should not exceed 10 VED percentage points for each of the three vaccine antigens.

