# **Primary objective**

**Primary Immunogenicity**: To evaluate the immunological non-inferiority seroconversion rate and Geometric Mean Titre (GMT) of the GPO seasonal trivalent split, inactivated influenza vaccine compared to active comparator vaccine for each of the three vaccine antigens at three weeks after immunization (Day 21).

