#### **11.2 Sample size calculation**

The sample size calculation was planned for a ratio of 2:1 between GPO Tri fluvac and active comparator vaccine respectively. The SAS 9.4 statistical software, was used to calculate the sample size needed for the study under the assumption of a non-inferiority trial for binary outcome endpoint.

According to the EMA recommendations for the co-primary endpoints, the sample size calculation was basing on the following primary endpoints:

- The difference in seroconversion rate of active comparator vaccine and Seroconversion rate of GPO Tri Fluvac should not exceed 10 percentage points.
- The difference in natural log of mean antibody titer between active comparator vaccine and GPO Tri Fluvac should not exceed 0.405, which is equivalence to the margin for GMT ratio = 1.5.

The sample size calculation was calculated using parameters of the three strains of influenza under the study, including H1, H3, and Flu B. The estimates for seroconversion and standard deviation of natural log of antibody titer were obtained from previous study, phase II study of GPO Tri Fluvac.

Influenza strain	Titer Visit	Treatment Group	Sero- conversion	Mean of ln(titer)	SD of ln(titer)
H1	Day 21	Vaccine	0.88	5.9728	1.08277
Н3	Day 21	Vaccine	0.535	5.36976	1.11926
Flu B	Day 21	Vaccine	0.865	4.75286	1.23306

The sample size calculation for non-inferiority test for proportions was performed with the margin of 0.1, assuming different seroconversion rate of the three influenza strain, and expected difference VED in seroconversion of the two groups is 0.000 with one-sided test alpha level 0.025 and power 0.8. VED Finally the sample size was adjusted for 7% not included in the ATP cohort. The required sample MITTEE size for this co-primary endpoint reached a total of 945 subjects: 630 for study vaccine group and cal MEDICINE 315 for comparator vaccine group.

wo group test of equivalence in proportions (targe unequal n s)				
	H1	H3	Flu B	
Test significance level, α	0.025	0.025	0.025	
(one- sided)				
Standard proportion, $\pi_{S}$	0.880	0.535	0.865	
Equivalence limit difference,	0.100	0.100	0.100	
$\pi_{T}$ - $\pi_{S}$ , $\Delta_{0}$				
Test expected proportion, $\pi_T$	0.880	0.535	0.865	
Expected difference, $\pi_T - \pi_S$ , $\Delta_1$	0.000	0.000	0.000	
Power (%)	80	80	81	
ns	125	293	134	
n T	250	586	276	
Ratio: n T / n S	2.000	2.000	2.000	

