^d Geometric Mean Fold Rises (GMFR) is the geometric mean of the ratios of post - vaccination to the pre-vaccination (Day 0)

- Seroconversion rate, seroprotection rate and GMTs will be compared between Tri Fluvac and comparator group.

Measure	Study Croup	HAI Assay			
	Study Group	Flu A H1 antibody titer	Flu A H3 antibody titer	Flu B antibody titer	
Day 0					
GMT ^c	Tri Fluvac (N=)	XX.XX (XX.XX, XX.XX)	XX.XX (XX.XX, XX.XX)	XX.XX (XX.XX, XX.XX)	
	Comparator (N=)	XX.XX (XX.XX, XX.XX)	XX.XX (XX.XX, XX.XX)	XX.XX (XX.XX, XX.XX)	
Day 21					
Seroconversion Rate ^a	Tri Fluvac (N=)	XX.XX% (XX.XX%, XX.XX%)	xx.xx% (xx.xx%, xx.xx%)	xx.xx% (xx.xx%, xx.xx%)	
	Comparator (N=)	xx.xx% (xx.xx%, xx.xx%)	XX.XX% (XX.XX%, XX.XX%)	XX.XX% (XX.XX%, XX.XX%)	
Difference in Seroconversion Rate ^b		XX.XX% (XX.XX%, XX.XX%)	XX.XX% (XX.XX%, XX.XX%)	XX.XX% (XX.XX%, XX.XX%)	
GMT ^c	Tri Fluvac (N=)	XX.XX (XX.XX, XX.XX)	XX.XX (XX.XX, XX.XX)	xx.xx (xx.xx, xx.xx)	
	Comparator (N=)	xx.xx (xx.xx, xx.xx)	XX.XX (XX.XX, XX.XX)	xx.xx (xx.xx, xx.xx)	
GMT Ratio ^d		xx.xx (xx.xx, xx.xx)	XX.XX (XX.XX, XX.XX)	xx.xx (xx.xx, xx.xx)	
Day 90					
Seroconversion Rate ^a	Tri Fluvac (N=)				
	Comparator (N=)				
Difference in Seroconversion Rate ^b					
GMT ^c	Tri Fluvac (N=)				
	Comparator (N=)				

TREF 02: Summary of Non-inferiority Established Based on Seroconversion Rate Differences and GMT Ratios

GMT Ratio^d

Note: a Sero-conversion is defined as 4 fold rising titer from baseline (Day 0). Values are the percent of subjects in each group (with 95% CI).

^b Percent difference in Seroconversion rate (with 95% CI). Clinical margin ≤ 10 %

^c Values are the geometric means titer (GMT) (with 95% CI) for the subjects in each group.

^d Values are the geometric means of the individual at Day 21 and Day 90 of Active comparator vaccine/ GPO Tri Fluvac HAI ratio. Clinical margin ≤ 1.5

- Non-inferiority criteria based on GMT ratio if the ratio for each HI assay at ≤ 1.5 and / or difference of seroconversion rate at $\leq 10\%$ for the upper bound of the 95% CI.

Day	Antibody Titer	GMT Ratio [Comparator/ Tri Fluvac] (95% CI)	Non- inferiority (Upper bound of the two-sided 95% CI of GMT ratio ≤ 1.5)
Day 21	Flu A H1	x.xx (x.xx - x.xx)	Yes / No
	Flu A H3		
	Flu B		
Day 90	Flu A H1		
	Flu A H3		
	Flu B		

TREF 03: Summary Immunogenicity Result: GMT Ratio

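### The non-inferiority rule reads as GMT ratio and/or seroconversion in the SAP and the protocol summary, while the protocol body sets both as co-primary criteria, so a vaccine that fails one could be declared non-inferior

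*SAP*

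**What the plan says.** **The looser wording.** The SAP synopsis, under Inferential analyses, takes as its acceptance values a GMT ratio (comparator over Tri Fluvac) of at most 1.5 "and/or difference of seroconversion rate at" 10% or less, judged on the upper 95% bound. The notes to TREF 02, 03 and 04 and to FREF 15–18 repeat it: "and / or difference of seroconversion rate at". Protocol section 1 (summary, Inferential analyses) has the same rule.

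**The stricter wording.** Protocol section 3 (Study Hypothesis) lists two parallel requirements. The upper bound of the GMT ratio "should not exceed 1.5 for each of the three vaccine antigens", and the upper bound of the seroconversion difference must stay within 10 percentage points, again for every antigen. Section 11.3.1 (Assessment of immune response) states the seroconversion limit and then adds a second one: "For the other primary endpoint, the upper bound of the two-sided 95% CI on the ratio of the GMTs" has its own limit of 1.5. Section 11.2 introduces the sizing with "According to the EMA recommendations for the co-primary endpoints". On error control, section 11.3.1 says: "No multiplicity adjustment to the error rate, alpha, will be made".

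**Day 90.** The primary objective in the SAP synopsis and in protocol section 1 covers Day 21 and Day 90. In protocol section 3 it covers Day 21 only. TREF 02–04 and FREF 16 and 18 set out Day 90 non-inferiority results under the same and/or note.

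**The concern.** This sentence decides whether the trial succeeds. Read as *or*, each antigen has two routes to success, and a failure on one margin does not prevent the claim. Unadjusted alpha is sound when all tests must pass, but not when any one of two may carry the claim.

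The sample size makes the point sharper. H3 seroconversion drives enrolment of 945; the GMT endpoint needs only 354. Under *or*, the test the trial was sized for becomes optional, and the claim can rest on a GMT test that is heavily over-powered when the two vaccines are truly alike.

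Nothing in the SAP settles the choice. TREF 03 and 04 give separate Yes/No results by antigen and day, and no statement combines them. The reading could therefore be chosen after the results are known.

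**Working it through.** **Inputs.** Protocol 11.2: one-sided alpha 0.025, power 0.80, 2:1 allocation, seroconversion margin 0.10, log-GMT margin 0.405, H3 seroconversion 0.535, H3 SD of ln(titre) 1.119, evaluable 293 comparator and 586 Tri Fluvac. Protocol Table 1: H3 Day 0 GMT 51.16 (43.43–60.27) in 200 vaccinees.

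**1. Reproduce the plan's figure.** Comparator n = (1.960 + 0.842)² × 0.535 × 0.465 × (1 + 1/2) / 0.10² = 293, so 586 on Tri Fluvac and 879 in total, as stated. 879/0.93 = 945.2, against 945 stated.

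**2. Power by criterion at 293:586, true difference zero.**
- H3 seroconversion: SE = √[0.535 × 0.465 × (1/293 + 1/586)] = 0.0357; Φ(0.10/0.0357 − 1.96) = 80.0%.
- H3 GMT: SE = 1.119 × √(1/293 + 1/586) = 0.0801; Φ(0.405/0.0801 − 1.96) = 99.9%.
- Seroconversion for H1 and B: 99.0% and 98.3%. GMT for H1 and B: 99.9% and 99.6%.

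**3. One data set, two conclusions (H3).**
- Seroconversion 53.5% comparator, 47.5% Tri Fluvac: SE = √(0.535 × 0.465/293 + 0.475 × 0.525/586) = 0.0357; upper bound 0.060 + 1.96 × 0.0357 = 13.0 points. Fails.
- GMT ratio 1.15: upper bound exp(ln 1.15 + 1.96 × 0.0801) = 1.35. Passes.

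*Or* declares non-inferiority; *and* does not.

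**4. Chance that H3 passes on GMT alone**, Φ((0.405 − ln R)/0.0801 − 1.96):

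| True GMT ratio R | 1.0 | 1.1 | 1.2 | 1.25 |
|---|---|---|---|---|
| Pass | 99.9% | 97.2% | 79.4% | 62.2% |

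**5. Both endpoints exactly at their margins, one antigen.** If the tests are independent, the either/or rule passes 1 − 0.975² = 4.94% of the time, against 2.5% for one test. From the bivariate normal it passes 4.5% at correlation 0.5 and 3.9% at 0.8.

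**6. True H3 seroconversion deficit of exactly 10 points.** Simulation used bivariate log-normal Day 0 and Day 21 titres, two-fold dilutions, values below 10 set to 5, Day 21 SD 1.119, and the mean calibrated to 53.5% seroconversion. Baseline SD = ln(60.27/43.43)/(2 × 1.972) × √200 = 1.175. The test arm was shifted until the true deficit was 10 points. The documents give no pre/post correlation r, so it is assumed. Ranges cover repeated runs.

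| r | Implied true GMT ratio | Either/or passes |
|---|---|---|
| 0.2 | 1.43 | 9–12% |
| 0.4 | 1.37 | 21–23% |
| 0.6 | 1.29 | 45–47% |

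Seroconversion alone passes 2.2–2.5%, and requiring both passes 0.7–2.1%. As a cross-check, the step 4 formula at these ratios gives about 9%, 20% and 47%, so nearly all the either/or passes come through GMT.

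**7. Power if all six tests must pass, true difference zero.** The product under independence is 77.5%. The lower limit under any correlation is 1 minus the sum of the six failure probabilities, 76.8%. The upper limit is the weakest test, 80.0%.

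**The case against.** *And/or* includes *and*, and no passage uses the word both. The strict rule is inferred from the parallel limits, the co-primary label and the unadjusted alpha. That is correct: the defect is wording that permits the weaker rule, not a stated plan to use it. Nor did the SAP loosen the protocol. It carries over the protocol's own summary, so the protocol contradicts itself. For that reason, appeal to the protocol as the governing document does not resolve the matter.

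A failed criterion would still be visible, because TREF 02–04 show every interval and every Yes/No result. That stands; the exposure is in the overall claim.

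On Day 90, both synopses define the primary endpoint at Day 21, and protocol 11.5 places the primary analysis there. The conflict lies in the synopsis objectives and the table shells, and is the smaller issue.

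On size, near-100% GMT power holds only if the true ratio is near 1. The 62% at a ratio of 1.25 is not a false-claim rate: in the simulation model the true seroconversion deficit there is about 6–9 points, inside the margin. The 9–47% figures count as errors only if both criteria are required. The model also fits imperfectly. At the documented H3 GMTs (51.16 and 214.81) it predicts 61–64% seroconversion, and matching 53.5% needs a Day 21 GMT near 162–165. These percentages illustrate the problem and are not forecasts. Step 3 needs no such model.

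**Conclusion.** The concern holds. As written, the decision rule allows opposite primary conclusions from the same data, and neither document settles which applies. The protocol's hypothesis, co-primary label and unadjusted alpha all point to requiring both criteria for each antigen.

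The size depends on what is assumed. With both H3 endpoints at their margins, the error rises from 2.5% to 3.9–4.9% across correlations of 0.8 down to 0. With seroconversion truly 10 points worse and GMT still within its margin, the either/or rule passes roughly 9% to 47% of the time over assumed pre/post correlations of 0.2 to 0.6, against about 2.4% for seroconversion alone. This must be fixed before the results are interpreted.

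**What to change.** In the SAP synopsis, the notes to TREF 02–04 and FREF 15–18, and protocol section 1, replace the and/or sentence with one rule, for example:

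*Non-inferiority is concluded only if, at Day 21 in the ATP cohort, the upper limit of the two-sided 95% CI is at most 1.5 for the GMT ratio (comparator/Tri Fluvac) and at most 10 percentage points for the seroconversion difference (comparator minus Tri Fluvac), for all three antigens. All six tests, each at one-sided 0.025, must pass; no multiplicity adjustment is therefore needed.*

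Add one overall conclusion line to TREF 02. Align the primary objective in both synopses with protocol section 3, and label the Day 90 comparisons secondary, with no bearing on the conclusion.

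The cost is wording only: no new data and no change in sample size. With no true difference, joint power is 76.8–80.0%, at most about 3 points below the 80.0% for H3 seroconversion alone.
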